3.1. Informed Consent / Subject enrollment

Potential subjects will be identified from the patients presenting at the clinic. Additionally, an ad will be placed in the local newspaper and in the practice website. Once identified as a study candidate, the patient will be asked if he/she would like to participate. The sub-investigator, study coordinator or an appropriately trained staff member will answer any and all questions and will obtain informed consent. A copy of the signed informed consent document will be given to the subject. The principal investigator will be available if the subject wants to discuss further details with him. Any testing that is part of the investigative site's standard preoperative cataract evaluation may be performed prior to the informed consent being signed, provided these tests are conducted within 90 days of surgery. The patient will

understand that participation in the study, or declining to participate, will not affect his/her quality of care.

No subject will be enrolled into the study that does not meet the inclusion/exclusion criteria and does not sign the current approved informed consent document. Informed consent will be obtained prior to collecting any data for the study. The original signed documents will be maintained by the investigator as a permanent part of the subject's research records and a scanned copy will be uploaded to the subject's electronic medical record.

3.2. Surgery Procedures:

Patients will be randomized to one of two groups:

- Group A, plano OU. The target refraction for both eyes will be emmetropia (± 0.25 D).
- Group B, nano-vision. The target refraction for the dominant eye will be plano and for the non-dominant eye -0.50 ± 0.16 D.

3.3. Study Visit Schedule and Assessments (Table 1).

1. Visit Schedule: Subjects will be examined at the following intervals:

1. Visit 1: Screening and enrollment: Preoperative evaluation completed not more than eight weeks before surgery
2. Visit 2: Day of Surgery
3. Visit 3: Day 1: (12 to 48 hours) after surgery
3. Visit 4: Month 1: 30 ± 5 days postoperative after second eye surgery
4. Visit 5: Month 3: 90 ± 15 days postoperative after second eye surgery

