5. STATISTICAL CONSIDERATIONS

5.1. Sample size

The sample size estimates depend in large part on the standard deviation (SD) for logMAR UCVA. Assuming a SD of 0.16 (mean from previous Symfony studies)), for the two-sided t-test (alpha =0.05) for the near visual acuity endpoint, we will need 55 subjects in each group (emmetropia / nano-vision) to detect differences of 0.1 logMAR with 90% power. Total sample size = 110. Allowing 10 % for the potential confounding factor of having 4 sites, 120 subjects will be enrolled (60 in each group). Table 2 summarizes the sample size estimate.

Table 2. Sample size estimate.

	Toric Group	
	Emmetropia	Nano-Vision
Sample size	55	55
5% multiple sites	5	5
Total sample size	60	60

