5.2. Statistical Analysis

All data will be collected by the site and entered into a database. Subjects will be assigned an ID number. Data analysis will be performed without patient identification. Statistical analysis will be performed using standard descriptive statistics and other tests as deemed appropriate based on the characteristics of the data to be analyzed. All statistical tests will be two-sided and interpreted at a 5% significance level. Comparisons between the groups will be made. Data analysis will be conducted by a third party consultant.

5.3. Study Endpoints:

Comparisons between the groups:

1. Primary Endpoints:

- Binocular distance-corrected near (40 cm) visual acuity.

- Reduction of astigmatism.

2. Secondary Endpoints:

- Uncorrected and distance-corrected near (40 cm) visual acuity at 1 month and 3 months
- Uncorrected and distance-corrected intermediate (66 cm) visual acuity at 1 month and 3 months
- Uncorrected and best-corrected distance (4 m) visual acuity at 1 month and 3 months
- To evaluate patient's overall satisfaction of their vision
- To evaluate patient's spectacle independence
- To evaluate visual symptoms using a questionnaire.
- Residual mean spherical equivalent refraction at 1 and 3 months
- Residual refractive sphere at 1 month and 3 months
- Residual refractive cylinder at 1 month and 3 months
- Percentage of eyes with postoperative MRSE accuracy to target $\leq 0.5\text{D}$ at 1 and 3 months
- Determine stability of toric iol from time of surgery to 3 months postoperative
- To evaluate the surgeons experience and overall satisfaction

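### Residual MRSE and sphere are compared between groups without reference to the assigned targets, which differ by about 0.25 D on average, and per-eye endpoints have no stated handling of two eyes per subject

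*Combined protocol and SAP*

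**What the plan says.** Section 3.2 randomizes each subject to one of two groups. Both eyes of a Group A subject are aimed at emmetropia. In Group B, "The target refraction for the dominant eye will be plano and for the non-dominant eye -0.50 ± 0.16 D". Both eyes of a subject are therefore always in the same arm.

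Section 5.3 places all endpoints under a heading that announces between-group comparisons. Three matter most here:

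- "Reduction of astigmatism", a primary endpoint, with no unit of analysis.
- "Residual mean spherical equivalent refraction at 1 and 3 months", a secondary endpoint, with no unit and no reference to target. Residual sphere is listed in the same way.
- "Percentage of eyes with postoperative MRSE accuracy to target", within 0.5 D at 1 and 3 months. This is the only endpoint that names the eye as its unit.

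Residual cylinder and toric lens stability are also listed without a unit. On method, Section 5.2 says that "All statistical tests will be two-sided and interpreted at a 5% significance level" and otherwise leaves the tests to be chosen to suit the data. It names no method for fellow eyes. Section 5.1 counts subjects, and Section 5.4 compares proportions of patients.

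**The concern.** There are two separate problems.

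The first is the comparison of raw MRSE and sphere. The randomized intervention is the refractive target of one eye. Residual refraction not expressed relative to target has that target built into it, so the hypothesis of no group difference is false before any patient is operated on. A small P value would confirm that surgeons aimed where they were told to aim. A reader could take it for a difference in refractive accuracy.

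The second is the unit of analysis. The accuracy endpoint has up to 120 eyes per group as its denominator, from 60 randomized subjects. Reduction of astigmatism, cylinder and lens stability are naturally measured eye by eye. Because both eyes of a subject share an arm, positive correlation between them does not cancel in the group comparison. A test that counts eyes as independent would have standard errors that are too small. This matters most for reduction of astigmatism, because it is listed as primary.

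**Working it through.** **Inputs from the documents.** 60 subjects enrolled per group, two eyes each (Sections 2.2 and 5.1); targets as in Section 3.2; two-sided 5% level (Section 5.2).

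**Assumed, because the documents give no figure.** Inter-eye correlation ρ of 0.3, 0.5 and 0.7; SD of residual refraction per eye of 0.4, 0.5 and 0.6 D.

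**Step 1. The plan's own figure.** "Assuming a SD of 0.16 (mean from previous Symfony studies" and a difference of 0.1 logMAR, the normal formula gives n = 2 × (1.960 + 1.282)² × 0.16² / 0.1² = 53.8, so 54 per group. The exact t-test has power 89.6% at 54 and 90.1% at 55. The stated "55 subjects in each group (emmetropia / nano-vision) to detect differences of 0.1 logMAR with 90% power" reproduces. It concerns subjects and near acuity, so nothing below touches it.

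**Step 2. Difference built into raw MRSE.** Mean target over both eyes:

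- Group A: (0 + 0)/2 = 0 D
- Group B: (0 - 0.50)/2 = -0.25 D

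The expected difference is 0.25 D, or 0.50 D for non-dominant eyes alone. The same shift applies to sphere if cylinder is similar in the two groups. It does not apply to cylinder itself.

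**Step 3. Chance that a 5% test flags it.** Use subject means, so that this step does not depend on how fellow eyes are handled. The SD of a subject's two-eye mean is SD × √((1+ρ)/2), and the standard error of the group difference is that value × √(2/60). With SD 0.4 and ρ 0.5: 0.4 × √0.75 = 0.346; 0.346 × 0.1826 = 0.0632; 0.25/0.0632 = 3.95; power = Φ(3.95 - 1.96) = 97.7%.

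| SD per eye | ρ = 0.3 | ρ = 0.5 | ρ = 0.7 |
|---|---|---|---|
| 0.4 D | 98.9% | 97.7% | 96.0% |
| 0.5 D | 92.5% | 88.5% | 84.4% |
| 0.6 D | 80.8% | 75.0% | 69.7% |

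**Step 4. Error from own target instead.** With equal true accuracy in both groups, simulated subject-level tests of signed error from each eye's target rejected in 4.7% to 5.5% of trials (SD 0.3 to 0.6 D, ρ 0.3 to 0.8).

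**Step 5. Eyes counted as independent.** The variance is understated by the factor 1+ρ, so the true type I error is 2 × (1 - Φ(1.96/√(1+ρ))):

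| ρ of analysed variable | 1.96/√(1+ρ) | Type I error | 120 eyes worth |
|---|---|---|---|
| 0.3 | 1.72 | 8.6% | 92 |
| 0.5 | 1.60 | 11.0% | 80 |
| 0.7 | 1.50 | 13.3% | 71 |

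**Step 6. The within-0.5 D endpoint.** This is a yes/no outcome, so the scale of ρ matters. If ρ is the correlation of signed refractive error (bivariate normal, centred on target, true rate 80% to 90%), the correlation between the two yes/no outcomes is about 0.06, 0.16 and 0.32 to 0.34 for ρ of 0.3, 0.5 and 0.7. Putting these into the Step 5 formula gives about 5.7%, 6.9% and 8.9 to 9.0%. The larger Step 5 figures apply only if 0.3 to 0.7 is the correlation of the yes/no outcome itself.

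**The case against.** The strongest reply is that the plan is silent rather than wrong. It nowhere says that eyes will be treated as independent, and its allowance for tests suited to the data leaves room for a clustered method. This stands: the type I error figures are conditional on an analysis that the plan permits but does not prescribe. A reader might infer that the per-eye tests are already too liberal, and the documents do not support that.

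A reader might also infer that mixed targets bias every refractive endpoint. They do not. The within-0.5 D endpoint is already scored against target, so only the correlation point reaches it; cylinder, astigmatism and lens stability are not shifted by the spherical target either.

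Nor is a significant MRSE result certain. The difference is there by design, but whether it reaches significance depends on an SD that the documents do not give.

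Finally, raw MRSE is worth reporting, since it shows whether the arms were separated. That is a reason to describe it, not to test it as an outcome. Silence on method does not answer this point: any valid test of raw MRSE or sphere between the groups has the 0.25 D built in.

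**Conclusion.** The point holds in two parts, and the plan should be changed.

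First, the between-group comparison of residual MRSE and sphere, as listed, compares quantities that differ by about 0.25 D by assignment. This follows from Sections 3.2 and 5.3 alone. That a test would probably be significant rests on the assumed SD and correlation in Step 3.

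Second, the plan defines one endpoint on eyes, leaves the unit open for others including a primary, and does not say how two eyes of one subject will be handled. Under an independent-eyes analysis the nominal 5% would become roughly 9% to 13% for a continuous endpoint and 6% to 9% for the within-0.5 D endpoint, if the correlation of the measured refraction lies between 0.3 and 0.7.

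Neither part reaches the binocular near-acuity primary, which has one value per subject, or the sample size.

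**What to change.** In Section 5.2, make the subject the unit of inference. Analyse every per-eye endpoint, including reduction of astigmatism, with a method clustered on subject. GEE with robust standard errors, a mixed model with a subject effect, or a subject-level mean would each serve; name one before data are seen.

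In Section 5.3, define MRSE and sphere for between-group testing as signed error from that eye's assigned target, and say that the within-0.5 D endpoint uses the same eye-specific target. Report raw MRSE and sphere descriptively only, by dominant and non-dominant eye, as a check that the arms were separated.

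Record ocular dominance in both groups before assignment. It is not among the Visit 1 assessments or in Table 1, and without it eye role is undefined in Group A.

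The cost is SAP wording and one recorded field, with no change to the number of subjects. Confidence intervals for per-eye endpoints would be wider than under an independent-eyes analysis by √(1+ρ), that is by 14%, 22% or 30% for a correlation of 0.3, 0.5 or 0.7 in the analysed variable. That extra width reflects the information that the trial actually has.

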5.4. Safety Analyses

The type, severity, duration and frequency of reported ocular adverse events will be tabulated for each group. Adverse events will also be summarized for events that were considered treatment-related. Comparison of treatment groups with respect to the proportion of study patients reporting adverse events will be made using Fisher's Exact Test.

6. DATA HANDLING AND RECORD KEEPING

6.1. Confidentiality

To ensure confidentiality in this study, records of the participants will be examined only by the principal investigator and research staff involved in the study. Study records will be kept on file at each site. Any statistical analysis and publication will not include any subject identifiers. Medical records will be made available only for review by the investigators, study Monitor or Auditor, Sponsor Company or Research Institution, the IRB, and other State or Federal Regulatory Agencies, if necessary. All information in these records will be kept confidential.

6.2. Records Retention

The PI is accountable for the integrity, retention and security of all study related data. The investigator must maintain accurate, complete and current records relating to the clinical study. The investigator must maintain the required records during the investigation and for a period of 1 year after the date on which the investigation is terminated or completed.

7. STUDY MONITORING, AUDITING, AND INSPECTING

The nature and location of all source documents will be identified to ensure that original data required to complete the case report forms (CRFs) exist and are accessible for verification by the monitor. If electronic source records are maintained, these records must be 21 CFR Part 11 compliant and will be printed and certified for verification by the monitor as needed.

Required examination must be recorded on the CRFs. Provided CRFs can be used as source document. All data reported must have corresponding entries in the source documents. The principal investigator or sub-investigator must review the reported data and certify that the CRFs are accurate and complete. No subject identifiers should be recorded on the CRFs beyond subject number, subject initials and study specific identifiers.

Data from CRFs will be entered into a database provided to each site, site will email the password protected file to the study manager with the CRFs for remote monitoring. Additionally, monitoring site visits will be made by the study manager throughout the study.

Upon completion of the CRFs, the data will be reviewed by study manager and statistician for accuracy and completeness. If corrections and/or any additions to the data are deemed necessary, queries will be generated and forwarded to the investigative site. Designated research staff expected to respond to data queries in a timely manner and ensure that the corrections and changes made to the data in the database are reflected in the subjects' source documentation. Any changes will need to be initialed and dated by the authorized personnel making such changes.

Data will not be sold to third parties nor will it be used for future research.

Electronic data will be stored and accessed on a portable device. The laptop is password protected and only the study manager has access to it. Additionally, database will be password protected.

8. INVESTIGATIONAL PRODUCT

8.1. Description

The Symfony Toric IOL (ZXTx) is an extended depth of focus (EDOF) IOL design to improve the sharpness of vision at near, intermediate and far distances reducing the need of glasses after cataract surgery in patients with astigmatism. The EDOF IOL, similarly to a monofocal IOL, has one

focal point, it is elongated in the EDOF, having less of a halo and glare problem compared to multifocal IOLs.

8.2. Treatment/Dosing Regimen

The Symfony Toric IOL (ZXTx) is intended for primary implantation for the visual correction of aphakia secondary to removal of a cataractous lens in adult patients. The IOL will be implanted at time of uncomplicated routine cataract surgery. Intraocular lenses are implantable medical devices and are intended for long term use over the lifetime of the patient.

8.3. Method for Assigning Subjects to Treatment/Dosing Groups

The statistician will provide randomization envelopes. The envelopes will be sequentially numbered and they will be provided to each site.

8.4. Subject Compliance Monitoring

Since the IOL is implanted at time of cataract surgery, subject compliance will not be an issue in this particular study.

8.5. Packaging, Receiving, Storage, Dispensing and Return

An account will be set up with the manufacturer of the lens (Abbott Medical Optics - AMO) that will provide the lens at no cost to the participants. IOLs will be ordered once the subjects qualification for the study has been confirmed. IOLs will be shipped to the site or ambulatory surgery center and will be stored and dispensed following the routine standard of care for cataract surgery. Unused IOLs will be returned to AMO following their instructions.

9. ETHICAL CONSIDERATIONS

This clinical trial will be conducted in accordance with the principles of the Declaration of Helsinki, and Good clinical practice. The Investigator and all clinical trial staff will conduct the clinical trial in compliance with this protocol. The Investigator will ensure that all personnel involved in the conduct of the clinical trial are qualified to perform their assigned duties through relevant education, training, and experience. Deviations from the clinical protocol must be documented in each subject's study records including the dates and reasons for each deviation. The PI must ensure that all aspects of the trial are in compliance with the applicable regulatory laws and conditions of approval imposed by the IRB.

10. IN CASE OF AN INJURY RELATED TO THIS RESEARCH STUDY

Every effort to prevent study-related injury will be taken by the study doctor and staff. In the event a patient is injured as a direct result of the study while following the study instructions and requirements, the patient will be instructed to immediately contact the principal investigator and/or study staff. Treatment will be provided as needed for those injuries caused directly by this research

study. In the event of injury or illness caused by or occurring during the participation in this study, all charges for medical care provided will be billed to the patient's insurance company. The medical care costs for injuries or illnesses that are not caused directly by the research study will not be covered.

